7.2.2. Exclusion Criteria

Subjects will be excluded if they fulfill any of the following exclusion criteria:

- 1. Previous infection with SARS-CoV-2.
- 2. Receipt of any vaccine for the prevention of COVID-19 (single or multiple doses).
- 3. A SARS-CoV-2 infection symptom score greater than 0 in any of the 4 catergories (fever, cough, shortness of breath or fatigue) at the time of screening (Ordinal Scale for Clinical Improvement score of 0).
- 4. Known history of chronic pulmonary disease (e.g., asthma [including atopic asthma, exerciseinduced asthma, or asthma triggered by respiratory infection], chronic pulmonary disease, pulmonary fibrosis, COPD), pulmonary hypertension, or heart failure.
- 5. Any condition which, in the opinion of the Principal Investigator, would prevent full participation in this trial or would interfere with the evaluation of the trial endpoints.

7.3. Study Integrity

This will be a double-blind study randomized 1:1 PUL-042 Inhalation Solution: placebo.

7.4. Number of Subjects

Approximately 200 subjects (100 Pul-042 Inhalation Solution: 100 placebo) will be enrolled.

7.5. Number of Study Sites

There will be up to 20 study centers.

7.6. Duration of Subject Participation

Subjects will participate for approximately 28 days.

7.7. Schedule of Study Activities

The schedule of events is presented in Table 1.

Table 1:Schedule of Events

Event	Screening	Dose 1 ^a	Dose 2, 3, 4 ^a	Follow-up/Early Discontinuation from Study	Study Completion
	V1	V2	V3, 4, 5	V6	V7
	Day -2 to Day 1	Day 1 ^b	Days 3, 6, 10	Day 15	Day 29
Informed consent	X				
Medical history	Х				
Pregnancy test ^c	Х			Х	Х
Physical exam	Х	Х	Х	Х	
Vital signs ^d	Х	Х	Х	X	
Spirometry ^e	Х	Х	Х		
Symptom score ^f	Х	Х	Х	X	Х
SARS-CoV-2 test ^g		Х		X	Х
Study drug administration ^h		Х	Х		
Adverse events	Х	Х	Х	X	Х
Concomitant medications	Х	Х	Х	X	Х
Ordinal Scale for Clinical Improvement	X	Х	Х	Х	Х
Randomization	Х				

^a Vital signs, adverse events, and concomitant medications will be assessed prior to administration of study medication and also at 30 minutes post-dose.

^b There is no Day 0 in this study

^c Urine pregnancy test or serum pregnancy test if women are of child-bearing potential. If urine pregnancy test is positive, a serum pregnancy test must be done. Pregnancy test is required for Early Discontinuation, not Day 15.

^d Vital signs will include body temperature, blood pressure measurements, heart rate, and respiratory rate.

^e Spirometry will be done at screening to document eligibility. On days of dosing, spirometry will be done pre-dose and at 30 minutes (± 15) minutes post-dose. If the FEV1 is reduced > 10% compared to the pre-dose baseline the FEV1 should be repeated as clinically indicated

^fSARS-CoV-2 symptoms will be assessed at each visit according to the Symptom Score

^g SARS-CoV-2 testing will be performed pre-dose on Day 1 (Visit 2), Day 15 (Visit 6) and at Day 29 (Visit 7). Additional testing should be conducted at any point during the study when clinical symptoms are suggestive of potential COVID-19.

^h Study drug administration must be done by a health care professional

7.8. Subject Participation

Subjects will be followed for the duration of the entire study (28 days) to assess the incidence of SARS-CoV-2 infection and progession to COVID-19. The following are general guidelines for study conduct:

- Subjects, including those in whom dosing is discontinued for any reason should complete all visits as outlined in the protocol.
- Subjects who test positive for SARS-CoV-2 during the study, prior to the completion of the dosing regimen, may continue to receive additional doses of study drug up to Day 10 if treatment continues to be well tolerated at the discretion of the Principal Investigator. Subjects who withdraw from dosing should complete the Early Discontinuation Visit and complete the assessments on Day 29.

7.9. Study Day -2 to Day 1 (Screening)

The following assessments will be conducted prior to performing any study-specific procedures:

• Informed consent: The subject will sign an informed consent form approved by the governing Institutional Review Board (IRB) or Ethics Committee.

Once the informed consent is obtained, the following will be conducted as part of Screening to document subject eligibility for the study.

- Medical history (including documentation of exposure to SARS-CoV-2)
- Physical examination (including height and weight)
- Vital signs
- Spirometry
- Serum pregnancy test or urine test (if urine test is positive, a serum test must be conducted)
- SARS- CoV-2 infection symptom score
- Concomitant medication assessment
- Ordinal Scale for Clinical Improvement
- Randomization to study treatment
- Adverse event (AE) assessment (AE collection starts at the time the time of randomization to study treatment and is continuous throughout the study until 28 days after receiving study drug)

7.10. Study Day 1

7.10.1. Day 1 (Pre-dose)

Assessments conducted during Screening do not have to be repeated if done on Day 1.

The following should be obtained prior to dosing.

• Physical examination

- Vital signs
- Spirometry
- Nasopharyngeal or oropharyngeal sample for SARS-CoV-2 testing
- Adverse event assessment
- Concomitant medication assessment
- SARS- CoV-2 infection symptom score
- Ordinal Scale for Clinical Improvement

7.10.2. Day 1 (Study Drug Administration)

Dosing

PUL-042 administration must be supervised by a health care professional. PUL-042 will be administered via a PARI Sprint nebulizer equipped with a filter valve to prevent aerosol generation. A nose clip will be used during the nebulization procedure. All doses will be administered as a constant volume (4 mL) via nebulization; the nebulizer will be operated until all drug has been delivered. All of the following time points are defined relative to the completion of dosing (T_0).

Post-Dose Guidelines

In previous studies with healthy volunteers, some subjects have demonstrated a transient decrease in lung function, usually asymptomatic. To date, subjects have recovered to at or near baseline lung function values without the administration of rescue medication. However, if after administration of PUL-042 Inhalation Solution there are clinical symptoms (increased respiratory rate, cough, shortness of breath) of decreased lung function, albuterol (salbtuamol) can be administered.

Following dosing, if a reduction of FEV1 >10% relative to pre-treatment is recorded, the subject should have the FEV1 measurement repeated as clinically indicated. If a reduction of FEV1 >12% relative to pre-treatment is recorded at 4 hours, the subject must be reviewed by the Principal Investigator prior to further dosing. If a reduction of FEV1 >12% relative to pre-treatment persists for up to 4 hours and is associated with clinical symptoms over this period, no further investigational treatment should be administered. Albuterol (salbutamol) may be given to symptomatic subjects at the discretion of the investigator.

If a reduction of FEV1 >20% relative to pre-treatment is recorded, no further investigational treatment should be administered to that subject.

7.10.3. Day 1 (T_0 +30 minutes [±15 minutes])

- Vital signs
- Spirometry
- Adverse event assessment
- Concomitant medication assessment

7.11. Study Days 3, 6, and 10 (Study Drug Administration)

All procedures should occur ±1 day from the scheduled Study Day.

7.11.1. **Pre-dose**

On Days 3, 6, and 10 the following dosing guideline should be observed prior to dose administration:

• At Investigator discretion, dosing can be HELD or STOPPED at any time for safety reasons.

The following should be obtained prior to dosing.

- Physical examination
- Vital signs
- Spirometry
- Adverse event assessment
- Concomitant medication assessment
- SARS- CoV-2 infection symptom score
- Ordinal Scale for Clinical Improvement

7.11.2. Days 3, 6, and 10 (Study Drug Administration)

Dosing

PUL-042 administration must be supervised by a health care professional. PUL-042 will be administered via a PARI Sprint nebulizer equipped with a filter valve to prevent aerosol generation. A nose clip will be used during the nebulization procedure. All doses will be administered as a constant volume (4 mL) via nebulization; the nebulizer will be operated until all drug has been delivered. All of the following time points are defined relative to the completion of dosing (T_0).

Note: Missed doses should not be replaced

Post-Dose Guidelines

In previous studies with healthy volunteers, some subjects have demonstrated a transient decrease in lung function, usually asymptomatic. To date, subjects have recovered to at or near baseline lung function values without the administration of rescue medication. However, if after administration of PUL-042 Inhalation Solution there are clinical symptoms (increased respiratory rate, cough, shortness of breath) of decreased lung function, albuterol (salbutamol) can be administered.

Following dosing, if a reduction of FEV1 >10% relative to pre-treatment is recorded, the subject should have the FEV1 measurement repeated as clinically indicated. If a reduction of FEV1 >12% relative to pre-treatment is recorded at 4 hours, the subject must be reviewed by the Principal Investigator prior to further dosing. If a reduction of FEV1 >12% relative to pre-treatment persists for up to 4 hours and is associated with clinical symptoms over this period, no further investigational treatment should be administered. Albuterol (salbutamol) may be given to symptomatic subjects at the discretion of the investigator.

If a reduction of FEV1 >20% relative to pre-treatment is recorded, no further investigational treatment should be administered to that subject.

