A similar potential pharmacodynamic effect was seen in the spirometry data (specifically the forced expiratory volume in 1 second [FEV1]) from PUL-042-001, likely due to the effect of PUL-042 on the bronchial airways. A dose-dependent decrease in FEV1 was seen with a nadir at approximately 30 minutes post-dose in subjects treated with PUL-042 Inhalation Solution. There was no comparable decline observed with placebo. These measurements were largely within the 12% change from baseline accepted as normal variability. This was followed by a recovery to near baseline levels at 24 hours post dose. Over the course of 7 days, the mean FEV1 was within 0-5% of the baseline value, with the subjects who received higher doses of PUL-042 showing a larger mean decrease in FEV1. None of the decreases in FEV1 were accompanied by signs of respiratory distress or a drop in oxygen saturation. None of the FEV1 results in the PUL-042 inhalation treated groups were statistically different from placebo after the 30-minute time point. The MTD delivered as a single dose was established as 40.6 µg Pam2 : 59.5 µg ODN in PUL-042-001.

A second phase 1 study (PUL-042-003) has been completed. PUL-042-003 was a randomized, open-label, cross-over study to determine the safety and tolerability of PUL-042 Inhalation Solution and to explore the effect of pretreatment with either cromolyn sodium or albuterol sulfate. The primary objective of this study was to determine the safety and tolerability in healthy normal subjects of single or repeated doses of PUL-042 in SWFI. Exploratory objectives include determining whether ANC was an indicator of biological activity and to determine 1) the duration of local biological activity in the bronchial airways by serial FEV1 measurements, 2) whether the administration of cromolyn sodium prior to the administration of PUL-042 had an effect on the FEV1 response, and 3) whether the administration of albuterol prior to the administration of PUL-042 had an effect on the FEV1 response.

In protocol PUL-042-003, the first cohort of 8 subjects (cohort 1) received a dose of 20.3 μ g Pam2 : 29.8 μ g ODN (1/2 the single-dose MTD of PUL-042) with or without pretreatment with cromolyn sodium (4 each). Subjects were then crossed over to the alternative treatment after a 2-week follow-up period and an additional 2-week washout period.

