2.2.3 Safety and Tolerability Endpoints

- Reduction in forced expiratory volume in 1 second (FEV1) from Pre-dose to Post-dose
- Treatment-emergent serious adverse events (SAEs) through Day 29
- Treatment-emergent adverse events (TEAEs) and severity through Day 29
- Vital signs

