7.3 Pulmonary Function Testing

Spirometry tests including FEV1 (L), % predicted FEV1, FVC (L), % predicted FVC and FEV1/FVC values will be collected at screening and FEV1 (L) will also be recorded at the time points presented in the Appendix A. FEV1 results will be summarized by presenting descriptive statistics of raw data of FEV1 (L) and percent change from each Pre-dose value to Post-dose value on the dosing days.

The proportion of subjects with percent decrease in FEV1 (L) from Pre-dose value to Post-dose value will be presented for each category: >10% and <=12% of reduction; >12% and <=20% of reduction; and >20% of reduction at each measurement time point (Day 1, Day 3, Day 6 and Day 10).

The percent change in FEV1 (L) from Pre-dose value to the protocol defined 30-min Post-dose values will be illustrated in a box/whisker graph on each dosing day by treatment group.

Spirometry results from unscheduled visits will be excluded from table summaries but will be included in the data listing.

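### After Day 1 the 20% FEV1 stop does not say which earlier value it is measured from, and on the same-day reading nothing limits decline relative to Day 1

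*Protocol*

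**What the plan says.** The post-dose guidelines in Protocol 7.11.2 carry the Day 1 text of 7.10.2 over to Days 3, 6 and 10. They contain four FEV1 triggers:

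- a fall above 10%: repeat the measurement as clinically indicated;
- a fall above 12% at 4 hours: review by the Principal Investigator before further dosing;
- a fall above 12% persisting for up to 4 hours with symptoms: no further treatment;
- a fall above 20%: "If a reduction of FEV1 >20% relative to pre-treatment is recorded, no further investigational treatment should be administered to that subject".

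In 7.11.2 all four are measured from *pre-treatment*. Other places bear on what that means:

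- **Protocol 7.7, Table 1, footnote e** schedules spirometry before dosing and at 30 minutes on each dosing day, then says: "If the FEV1 is reduced > 10% compared to the pre-dose baseline the FEV1 should be repeated as clinically indicated".
- **SAP 2.2.3** lists the endpoint as "Reduction in forced expiratory volume in 1 second (FEV1) from Pre-dose to Post-dose", and **SAP 7.3** summarises "percent change from each Pre-dose value to Post-dose value on the dosing days", with a category for falls above 20% on each dosing day.
- **Protocol 6.2** uses *pre-treatment* for the visit before the first dose.
- **SAP 4.6** defines baseline as the last value before the first dose.

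Protocol 7.11.1 requires spirometry before Doses 2 to 4 but attaches no FEV1 threshold to it. Its only dosing guideline is discretionary: "At Investigator discretion, dosing can be HELD or STOPPED at any time for safety reasons".

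**The concern.** On Day 1 only one pre-dose value can be the reference. From Day 3 there are two, and the trial may have up to 20 centers (Protocol 7.5), so the same reading could stop one subject and not another.

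The same-day reading has a second consequence: the reference resets at each dose. A subject who arrives below the Day 1 value starts a new 20% allowance from the lower level, and no FEV1 rule looks at the total. The 20% stop is also the only FEV1 stop that the scheduled readings can trigger alone, because no 4-hour reading is scheduled and the 12% stop also requires symptoms.

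Some features make drift worth considering. After a single dose in the first phase 1 study, "Over the course of 7 days, the mean FEV1 was within 0-5% of the baseline value"; the average decline grew with dose. A similar pattern was seen through 7 days in PUL-042-003, which used this trial's Pam2 dose. Doses 2 and 3 fall inside that first week. The studies in Protocol 5.4 gave two doses about 3 days apart, or four over 32 days, whereas this trial gives four in 10 days. Protocol 7.8 also allows subjects who become SARS-CoV-2 positive to continue dosing. Any FEV1 loss from infection would lower the same-day reference.

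**Working it through.** The plan gives no operating characteristics for the FEV1 rules, so there is no figure to reproduce.

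**1. Which reference?** Footnote e favours the same-day value but covers only the 10% repeat. SAP 7.3 favours it but governs summaries, not dosing. Protocol 6.2 and SAP 4.6 favour the value before the first dose, but neither concerns FEV1 stopping. The balance leans to the same-day value without settling it.

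**2. Largest fall that does not meet the stop (same-day reading).** Let *d* be the pre-dose deficit against Day 1. A same-day fall of exactly 20% does not exceed the limit, so the maximum is 1 − 0.80(1 − *d*).

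| *d* | Maximum below Day 1 | Same-day fall that reaches 20% below Day 1: 1 − 0.80/(1 − *d*) |
|---|---|---|
| 2.5% | 22.0% | 17.9% |
| 5% | 24.0% | 15.8% |
| 10% | 28.0% | 11.1% |

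The 5% row is the top of the mean range in Protocol 5.4. The 10% row is an assumption. Re-dosing is at issue only after Days 3 and 6, because Day 10 is the last dose.

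**3. Does another step catch these cases?** At *d* of 5% and 10% the missed same-day falls are 15.8–20% and 11.1–20%. All of them pass the 10% repeat step. Once *d* exceeds 1 − 0.80/0.90 = 11.1%, a same-day fall of 10% or less can already be more than 20% below Day 1, and no FEV1 step applies.

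**4. How often?** This cannot be derived from the documents, so the following is a range under assumptions.

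- Mean drift μ is 0 to 2.5% (Protocol 5.4 gives 0–5% across dose levels).
- The mean 30-minute fall *m* is 5%. No document gives this value.
- The SD of the difference between two readings is 3% to 6.1%. The upper value is 12%/1.96, taken from "These measurements were largely within the 12% change from baseline accepted as normal variability" on the assumption that 12% is a 95% limit.
- Noise per reading is σ = SD/√2, which is 4.3% at the upper value.

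Write each reading as a fraction of true Day 1 FEV1, with independent noise: Day 1 pre-dose *D₁* has mean 1, same-day pre-dose *Dₖ* has mean 1 − μ, and post-dose *P* has mean (1 − μ)(1 − *m*). A case is missed when *P* < 0.8*D₁* but *P* ≥ 0.8*Dₖ*. Both differences have SD σ√1.64 and their correlation is 1/1.64 = 0.61.

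For μ = 2.5% and SD 6.1%:

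- Against Day 1: mean 0.975 × 0.95 − 0.8 = 0.126, SD 0.0552, *z* = 2.29, so 1.11 per 100.
- Against the same day: mean 0.975 × 0.15 = 0.146, *z* = 2.65, so 0.41 per 100.
- Both: 0.11 per 100. Missed: 1.11 − 0.11 = **1.0 per 100 per dosing day**.

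Variations:

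- Zero mean drift: 0.3.
- A true between-subject SD of 3% added to the fall, at μ = 2.5%: SD √(0.0552² + 0.029²) = 0.0625, and 1.8 missed.
- SD 3% at μ = 2.5%: below 0.1, with or without that spread.

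Hence about 0 to 2 per 100. The result is sensitive to mean drift. At μ = 5% for every subject and SD 6.1%, the same model gives 3.0, or 4.3 with the added spread.

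**The case against.** The strongest reply is that the data in Protocol 5.4 do not show a cumulative problem. FEV1 recovered to near baseline by 24 hours, no treated group differed statistically from placebo after the 30-minute point, and no decrease came with respiratory distress or desaturation. The 0–5% range spans all dose levels with larger decreases at higher doses, and this trial uses half the single-dose maximum tolerated dose. In PUL-042-003 later decreases were sporadic and longer-term values were comparable to baseline. No section reports cumulative decline. This largely stands. Lack of statistical difference does not prove zero drift, but it supports a low frequency.

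Second, a same-day reference is the natural measure of acute bronchoconstriction, which is what the guideline addresses. This stands: the same-day choice is not an error.

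Third, other safeguards exist: the 10% repeat, the 12% review at 4 hours, examination and vital signs before each dose, investigator discretion, ongoing review of lung function (Protocol 13.5) and DSMB reviews at 40, 80 and 120 subjects (14.4). These are real but partial. Repeats are left to clinical judgment, and the 12% review depends on an unscheduled reading.

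A reader might infer more than the documents support in two ways. One is that the plan clearly intends the same-day value and so permits re-dosing at 24–28% below Day 1. The reference is open, and on the first-dose reading that consequence disappears. The other is a missed rate of up to 4.4 per 100 at 2.5% mean drift, obtained by treating drift and same-day fall as independent with SD 6.1%. If that SD is reading variability, the same pre-dose reading enters both quantities and forces a correlation near −0.5, so independence contradicts its own source.

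**Conclusion.** The point holds in a limited form. The reference for the 20% stop is undefined after Day 1, and the documents contain support for both readings. On the same-day reading, 24% and 28% below Day 1 are exact maxima for pre-dose deficits of 5% and 10%, and no FEV1 limit covers total decline. They are boundary values, not expected outcomes, and the protocol's *should* makes the stop slightly less than absolute.

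The frequency is unknown and probably low, about 0 to 2 per 100 active subjects on each of Days 3 and 6. That range rests on mean drift of at most 2.5%, an assumed 5% acute fall and noise shared between readings. The need to name the reference does not depend on it. This is a cheap improvement of low to moderate severity.

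**What to change.** In Protocol 7.11.2:

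1. Define *pre-treatment* as that day's pre-dose FEV1 for the 10% step and both 12% steps, in line with footnote e and SAP 7.3.
2. For the 20% stop, write: *relative to the higher of the Day 1 pre-dose FEV1 and that day's pre-dose FEV1*.
3. Apply the 20% stop to the scheduled pre-dose reading as well, so that a subject already more than 20% below Day 1 is not dosed.

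Section 7.10.2 and footnote e can stay, since on Day 1 the two values coincide. In SAP 7.3 keep the same-day categories and add one row per dosing day counting falls above 20% from the reference in item 2.

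The rule is never less protective than the same-day rule and needs no extra spirometry. The cost is a few extra stopped doses, mainly in the active arm. Some would come from measurement noise, because the higher of two noisy readings is biased upward, and some from COVID-19 itself.

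The model above was simulated with 2,000,000 subjects and fresh noise each day. A post-dose stop on Day 3 or 6 loses 2 or 1 doses, and a pre-dose stop on Day 3, 6 or 10 loses 3, 2 or 1. At 2.5% mean drift the extra loss is 0 to 5.5 of the active arm's 400 planned doses (100 × 4), at most 1.4%. With no drift and no drug effect it is about 0.1 at most. At 5% mean drift and SD 6.1% it reaches 9.8 to 13.5. Stopped subjects stay in follow-up to Day 29 (Protocol 7.13).

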7.11.3. Days 3, 6, and 10 (T_0 +30 minutes [±15 minutes])

- Vital signs
- Spirometry
- Adverse event assessment
- Concomitant medication assessment

7.12. Study Day 15 (Follow-up)

Assessments should occur within +1 day of target Study Day.

The following assessments will be conducted:

- Physical examination
- Vital signs
- Nasaopharyngeal or oropharyngeal sample for SARS-CoV-2 testing
- Adverse event assessment
- Concomitant medication assessment
- SARS- CoV-2 infection symptom score
- Ordinal Scale for Clinical Improvement

7.13. Early Discontinuation from Dosing and Study Withdrawal

Subjects who have received at least one dose of investigational treatment and are discontinued from dosing should continue to the final assessment at Day 29 according to the schedule of events specified for pre-dose assessments. There will be no post-dose assessments for these subjects.

Should the subject's study participation end prior to the completion of Study Day 15, the following assessments will be conducted as soon as possible after the decision to withdraw from the study is made.

- Physical examination
- Vital signs
- Serum pregnancy test or urine test (if urine test is positive, a serum test must be conducted)
- Nasaopharyngeal or oropharyngeal sample for SARS-CoV-2 testing
- Adverse event assessment
- Concomitant medication assessment

- SARS- CoV-2 infection symptom score
- Ordinal Scale for Clinical Improvement

7.14. Study Completion Day 29

Assessments should occur within +2 days of target Study Day.

- Serum pregnancy test or urine test (if urine test is positive, a serum test must be conducted)
- SARS- CoV-2 Symptom Score
- Adverse event assessment
- Concomitant medication assessment
- Ordinal Scale for Clincal Improvement
- Nasaopharyngeal or oropharyngeal sample for SARS-CoV-2 testing

